For consents conducted via telehealth, research staff will confirm the identity of the patient before signing the consent. Potential participants will confirm their identity by showing his/her driver's license or, if not available, any state or government-issued picture identification card. If they do not have picture identification available, they will be asked to provide the last four digits of the social security number, their date of birth and one of the following: account number, street address, insurance carrier name, insurance policy number, medical record number, birth certificate or insurance card.

Immediately following the consent, the research staff will send participants a REDCap link to complete the demographics form to be completed on the participant's own device or on the study iPad. The remaining baseline surveys will also be sent at this time if the first session is scheduled for within two weeks of the consent appointment. Otherwise the link to the remaining baseline surveys will be sent when it is within two weeks of Session 1.

Intervention Delivery

The program consists of an individual Integrative Health and Medicine (IHM) consultation with a CWH IHM provider, 4 Shared Medical Appointments (SMA) and 4 individual Health and Wellness Coaching (HWC) sessions. The SMA sessions take place at the UH CWH Beachwood office conference and movement rooms. The HWC sessions are virtual. The consultations are either virtual or in person at UH CWH Beachwood.

The following are the topics for each of the 8 weekly sessions:

| Week | Type of Session | Topic |
|-------------|------------------------------------|--|
| 1 | Shared Medical Appointment (SMA) | “NOURISH” with Nutrition experiential and cooking demo. |
| 2 | Health and Wellness Coaching (HWC) | Implement “NOURISH” education into patient’s personal life. |
| 3 | SMA | “MOVE” with Yoga experiential and exercise discussion. |
| 4 | HWC | Implement “MOVE” education into patient’s personal life. |
| 5 | SMA | “REST” with Meditation experiential and sleep discussion. |
| 6 | HWC | Implement “REST” education into patient’s personal life. |
| 7 | SMA | “INTEGRATE” with Acupuncture experiential and supplement discussion. |

| | | | |
|---|-----|---|--|
| 8 | HWC | Implement “INTEGRATE” education into patient’s personal life. | |
|---|-----|---|--|

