Participation in the program is not contingent participation in the outcome evaluation. Patients with a uterus aged 18-50 who have a fertility related diagnosis are eligible to participate in the program. Participants in the outcome evaluation will be a subset of the participants in the program who give their consent to researchers to collect survey and EHR data.

Data Collection

Data will be collected at baseline, at 4 weeks, 8 weeks, and before, after, and in between each of the 8 weekly sessions. Data collected at baseline include demographics, PROMIS Sleep Disturbance 8a, Perceived Stress Scale 4 (PSS-4), Infertility Self Efficacy Scale (ISE), and current Health Behaviors (HB). The HB survey will be administered between Sessions 1-8, as well as after Session 8, to observe any longitudinal changes. Patients will complete the PROMIS Sleep Disturbance 8a, PSS-4, and ISE at 4 weeks and 8 weeks. Pre- and post- session data includes 0-10 NRS ratings of stress, energy, focus, wellbeing, perceived support (post-only), and satisfaction (post-only). Additionally, participants will complete a satisfaction survey post Session 8. All data will be collected in REDCap via a text message or email link sent to the participant. Research staff will conduct a review of the participant’s medical record to collect data on the participant’s demographics and clinical characteristics at baseline, and to collect chemical pregnancy data at six months after the 8 sessions have been completed. This data will be entered into REDCap.

6. Study Timeline

| | Consent | Demographics | Baseline | 4 Week | Pre- & Post sessions | Between Sessions/After Session 8 | 8 Week |
|-------------------------------------|-----------|--------------|-----------|----------|--|----------------------------------|----------|
| Estimated time requirement of visit | 30-45 min | 2-3 min | 10-15 min | 8-10 min | Pre: 1 min x 8 Post: 2 min x 7, 6-8 min x 1 | 4-6 min x 8 | 8-10 min |
| Data Collection | | X | X | X | X | X | X |

7. Data to be Collected for Your Study (AFTER consent and HIPAA Authorization have been obtained)

We will collect pre-post outcome measures and satisfaction survey data. Please see attached surveys to be administered. We will also collect the following from the EHR:

- Age
- Sex

- History of mental health dx
- History of use Integrative Health and Medicine services
- Fertility diagnosis
- BMI
- Common comorbidities, including:
 - Hypertension
 - Diabetes
 - Obesity

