 - Ischemic heart disease
- Pregnancy as confirmed by presence of human chorionic gonadotropin (hCG) within 6 months of program completion

Attendance data about participants will also be collected.

8. Data Analysis Plan

Acceptability

Patients' responses on the satisfaction survey will be assessed using descriptive statistics.

Feasibility of Study Recruitment and Retention

We will use counts and percentages to summarize recruitment rates (#enrolled/#approached) and pace of accrual for the study, as well as retention rates of study participants (#attended/#enrolled) at each program session.

Demographics and clinical characteristics

We will use descriptive statistics (e.g. means, standard deviations, counts, and percentages) to summarize demographics (e.g., education level, age, income) and clinical characteristics (e.g., fertility-related diagnoses and duration of fertility treatment).

Effects on patient-reported outcomes

Descriptive statistics (e.g. means, standard deviations, counts, and percentages) will be generated for (1) patient-reported outcomes (PRO) collected at baseline, 4 weeks and 8 weeks (2) pre-and post-session NRS measures; and (3) responses to the health behavior survey. We will use linear mixed effects models to assess changes in quantitative measures of perceived stress, sleep disturbance, and self-efficacy over the course of the program. Means and bootstrapped 95% CI will be used to assess single-session effects on numeric rating scale measures of stress, energy, focus, and wellbeing. All statistical analyses will be conducted using R and RStudio.

Data Completeness

Data collected via REDCap at each time point will be evaluated for quality and completeness using reporting functions within REDCap.

9. Risks to Research Participants

Some of the questions might make participants feel uncomfortable. They may skip any questions that they may find upsetting.

There is a slight risk to losing privacy and confidentiality. All paper records will be kept in locked file cabinets and all electronic data will be stored in a password protected database to which only study staff will have access.

10. Provisions to Protect the Privacy Interests of Research Participants

Privacy will be ensured by conducting all study related interactions, including the consent process, within the private spaces, whether that is in person at the UH CWH clinic or remotely.

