Confidentiality of the research data will be protected in several ways. Any paper study documents will be stored in locked cabinets within the locked research offices of the PI and/or study staff. Participants will be identified by a separate study ID number on all study records. The lists that link study ID codes with participant names, and all electronic study records will be stored on password-protected, encrypted computers or secure servers. Only aggregate data will be presented or published, and will be presented such that individuals cannot be identified. Only IRB approved study personnel will have access to participant data. All study personnel will be required to be certified in the protection of human subjects throughout the study.

Identifiable information will not be reused or disclosed to any person or entity outside of University Hospitals other than those identified in the protocol, except as required by law, for authorized oversight of the research study, or as specifically approved for use in another study by the IRB.

11. Potential Benefit to Research Participants

There is no guarantee of benefits to any participant in the outcome evaluation, but the knowledge gained may be of benefit to future fertility patients who participate in the program.

12. Withdrawal of Research Participants

The study PI can withdraw participation of research participants at any time without their consent for the following reasons:

- If the subject fails to follow directions for participating in the study;
- If it is discovered that the subject does not meet the study requirements;
- If the study is canceled; or
- For administrative reasons, including competitive enrollment - the target number of subjects has entered the study.

13. Alternatives to Participation

The only alternative to participation in the research is to not participate. Patients can participate in the Lifestyle Care for Fertility program regardless of participation in the research.

14. Drugs or Devices

NA

15. Additional Information

NA

16. Community-Based Participatory Research

NA

17. International information

NA

18. References

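### Are the bootstrapped intervals for single-session effects too narrow because the plan does not say what is resampled?

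*Combined protocol and SAP*

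**What the plan says.** The analysis has one sentence, in Section 8 (Data Analysis Plan) under effects on patient-reported outcomes: "Means and bootstrapped 95% CI will be used to assess single-session effects on numeric rating scale measures of stress, energy, focus, and wellbeing". The sentence before it assigns a different method to a different question: "linear mixed effects models to assess changes in quantitative measures of perceived stress, sleep disturbance, and self-efficacy over the course of the program".

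The data behind the intervals are described in Section 5. Under Data Collection: "Pre- and post- session data includes 0-10 NRS ratings of stress, energy, focus, wellbeing". Under Intervention Delivery, the program has "4 Shared Medical Appointments (SMA) and 4 individual Health and Wellness Coaching (HWC) sessions". The Section 6 timeline lists the session surveys as "Pre: 1 min x 8 Post: 2 min x 7, 6-8 min x 1", which is 8 before and 8 after.

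No sample size is given. Section 12 refers to a point at which "the target number of subjects has entered the study" but attaches no figure. Nothing in the document states the correlation between one person's session changes, the resampling unit, the pooling level or the type of bootstrap interval.

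**The concern.** A bootstrap interval is valid only if the resampled units are independent. A participant who attends every session supplies 8 changes on each rating, and changes from the same person may well resemble one another. If an analyst stacked all sessions and resampled single rows, those 8 changes would be treated as coming from 8 people. The interval would be too narrow whenever the correlation is positive, and an immediate benefit of a session could be reported with more certainty than the data support.

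The contrast within Section 8 adds to the worry. It names a repeated-measures method for the perceived stress, sleep and self-efficacy scales, but nothing comparable for the session ratings. The type of interval is also open, and the simple percentile interval is known to be somewhat short in small samples.

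**Working it through.** The plan gives no interval width, power or sample size for this analysis, so there is no figure of its own to reproduce.

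**Inputs**
- Pairs per participant and rating: m = 8 if all sessions are pooled, 4 if pooled by session type, 1 if each session stands alone (Sections 5 and 6).
- Correlation between one person's changes, ρ: not stated; assumed 0.1, 0.3 and 0.5.
- Number of participants, n: not stated; assumed 10 to 40.

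**1. Pooled sessions, rows resampled.** With equal numbers of pairs and a common correlation, the variance of the pooled mean is inflated by DE = 1 + (m − 1)ρ, which row resampling ignores. The interval is 1/√DE of its proper width, and large-sample coverage is 2Φ(1.96/√DE) − 1.

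| m | ρ | DE | 1/√DE | 1.96/√DE | Coverage |
|---|---|---|---|---|---|
| 8 | 0.1 | 1 + 7×0.1 = 1.70 | 0.77 | 1.50 | 86.7% |
| 8 | 0.3 | 1 + 7×0.3 = 3.10 | 0.57 | 1.11 | 73.4% |
| 8 | 0.5 | 1 + 7×0.5 = 4.50 | 0.47 | 0.92 | 64.4% |
| 4 | 0.1 | 1 + 3×0.1 = 1.30 | 0.88 | 1.72 | 91.4% |
| 4 | 0.3 | 1 + 3×0.3 = 1.90 | 0.73 | 1.42 | 84.5% |
| 4 | 0.5 | 1 + 3×0.5 = 2.50 | 0.63 | 1.24 | 78.5% |

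Simulation with normal changes, m = 8 and n = 20 agrees: 86%, 72% and 61% at ρ = 0.1, 0.3 and 0.5.

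Two qualifications apply. The direction depends on the sign of ρ: at ρ = −0.05, DE = 1 − 7×0.05 = 0.65 and coverage is 98.5%, so the interval is too wide. The table also assumes complete attendance. With n = 20 and each pair present at random 75% of the time, simulated coverage is 88%, 77% and 69% at the three values of ρ; at 50% it is 90%, 83% and 75%.

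**2. Each session alone.** Here m = 1, so DE = 1 + 0×ρ = 1 for any ρ. Rows and participants are the same thing, and the choice of resampling unit disappears. Simulated percentile coverage over ρ from 0 to 0.5 is 89-90% at n = 10, about 93% at n = 20 and 93-95% at n = 40. This is a small-sample property of the percentile interval, which the plan does not in fact specify.

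**3. Which reading the text supports.** The sentence concerns the effect of a single session. Its neighbour reserves mixed models for change across the program, and the retention paragraph of Section 8 also works session by session. Separate analyses per session fit all three. Pooling is not excluded, but nothing in the text calls for it.

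**4. Whether prescribing another interval would help.** Bootstrap-t brings per-session coverage to about 94-95% for normal or well-spread ratings, at 1.31 times the percentile width for n = 10 and 1.11 times for n = 20. On whole-number 0-10 ratings, many people may report no change. Some resamples then have zero variance and the t-statistic is undefined. With an assumed 80% unchanged, simulated coverage is 65% for bootstrap-t against 88% for percentile at n = 10, and 85% against 92% at n = 15. These figures move with the assumed spread of the other 20% and with the handling of degenerate samples. Neither interval is better throughout.

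**The case for a change.** The strongest case for a change is that the three omissions are real and are not artefacts of the PDF. The phrase could also be read as the average immediate effect of a session, taken over all sessions. An analyst who took that reading and resampled rows would be following the sentence, and at ρ = 0.1 the error rate would already rise from 5% to about 13% (100 − 86.7). Stating the unit would cost one line.

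The omission and the arithmetic stand. The likelihood of the outcome is much weaker. It takes an unprompted decision to pool, followed by a choice of resampling unit that ignores the repeated-measures structure. The plan's authors use mixed models for the repeated scales in the same paragraph, so they are aware of that structure. The twofold difference in width (√4.50 = 2.12) is the extreme of an assumed range; at ρ = 0.1 it is √1.70 = 1.30.

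One point remains open under any reading. The four group appointments may induce correlation among people who attend together. The document does not say how many groups will run, so this cannot be sized, and resampling participants would not remove it.

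**Conclusion.** The concern does not call for a change. Section 8 leaves out detail, but its natural reading, one mean change per session with one pair per participant, carries no within-person clustering. What is left is coverage of about 90% at 10 participants and 93% at 20 instead of 95%, and only if a percentile interval is chosen. The larger losses (coverage of 64-87% with 8 pairs pooled, 78-91% with 4) require pooling, row-level resampling and positive correlation together. They also rest on assumed correlations and full attendance.

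The stakes are limited. This is an observational evaluation of a pilot program whose first objective is feasibility and acceptability. No hypothesis test, threshold or sample-size calculation uses these intervals. The only firm methodological alternative, bootstrap-t for every session, is a trade-off that can do worse on coarse ratings with many unchanged scores. An analyst can settle the remaining choices when writing the code and state them when reporting the results.
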